**4.D.2 Induction Period.** Eligible participants will take part in a 4-week induction period, during which they will engage in the VMRP procedure 3 times a week (Section 4.E.2) for providing urine samples. At each visit, they will receive 3 draws for prizes when they provide urine samples, regardless of whether the samples are positive for alcohol use. Those who provide at least 1 urine sample during each of these 4 weeks will receive a \$20 bonus incentive. Consistent with previous studies using this approach, only participants who demonstrate that they are frequent heavy drinkers and [continue to attend study visits] will be randomized. In our initial funding period, use of the induction period resulted in a CM completion rate of 65%, which exceeds published CM retention rates in non-SMI populations. Therefore, participants who 1) **attain an average EtG score of > 499 ng/mL** (indicating recent heavy drinking) and 2) **attend at least 1 study visit during the final week of the induction period** will be randomized. Given pilot data indicating that 53% of our sample during the initial funding period (n=42) had a mean induction EtG > 499 ng/mL, as well as our screening procedures to rule out light drinkers, we anticipate that at least 60% of the 400 consented participants (n=240) will be eligible for randomization. We will continue to recruit participants until 240 participants are randomized. Participants who do not meet criteria for randomization will be referred to other available AUD treatments.

**4.D.3 Randomization Procedures.** We will randomize 240 participants to treatment conditions by using permuted block randomization. We will stratify across the following variables: 1) study site, 2) gender, and 3) baseline EtG level > 1,000 ng/mL, which indicates very heavy recent drinking. [name] will randomize all participants to treatment conditions and will not have direct contact with participants.

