## **G. Data Analysis**

**4.G.1 General Data Analytic Strategy.** We will analyze outcome data in a manner consistent with previous RCTs of CM. We will analyze our primary and secondary outcomes longitudinally across the final 12-weeks of CM (when all reinforcers are contingent on alcohol abstinence) and the 6 month follow-up period to estimate the effects of CM. Below we discuss our strategy for the primary outcome of alcohol use, which is very similar to our strategy for Aim 2 outcomes. We will compute means and standard deviations for continuous variables and percentages and frequencies for categorical variables. Measures that fail to satisfy the assumptions of parametric tests will be transformed to adjust for differences in variability or skewness. Alternatively, nonparametric tests may be used. Our alpha threshold for statistical significance will be 0.05.

**4.G.2 Specific Data Analytic Techniques.** Groups will be compared for differences in demographics and pre-treatment drug and alcohol use, including data collected during the baseline interview and the 4-week induction period. We will **evaluate sex as a biological variable** by investigating whether sex moderates treatment outcomes. Comparisons will use analysis of variance (ANOVA) for continuous variables and chi-square tests for categorical variables (with Bonferroni-adjusted follow-up tests if necessary). Variables that differ between groups at baseline and during the induction period will be used as covariates in subsequent analyses, as will baseline measures that co-vary with the outcome measures.

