**Aims 1 and 2.** Recent alcohol use will be documented by using urine test results (binary outcome: EtG < 100 ng/mL or EtG > 100 ng/mL) and analyzed by using generalized estimating equations (GEE), generalized regression, and Cox proportional hazard regression techniques. Other outcome measures will be derived from recent alcohol use, such as 1) alcohol use (yes/no) over time; 2) longest duration of abstinence; 3) total number of periods of alcohol abstinence; 4) time to first alcohol abstinence; and 5) time to relapse after a specified period of alcohol abstinence. These outcomes will be examined across CM condition, time, and the CM condition-by-time interaction to determine whether one condition is superior to the others in promoting discontinuation of alcohol use. Additional analyses will be conducted by defining alcohol use in various clinically descriptive ways, such as the mean number of heavy drinking days or heavy drinking months across groups. Group comparisons of other Aim 2 outcomes will be assessed and evaluated in a similar fashion (e.g., longest duration of drug abstinence, mean HIV risk score).

Analyses will be conducted on the intent-to-treat sample (n=240). This is a conservative approach aimed at avoiding overestimation of the treatment effect. It includes all participants who were randomly assigned to treatment conditions, regardless of treatment completion. GEE models will be used to evaluate the differential change in primary and secondary outcomes by study condition over the 12-month study period (1 month before the baseline interview plus the 1-month induction, 4-month treatment, and 6-month follow-up periods), and whether condition interacts with change over time. This approach allows us to characterize between-group differences in longitudinal outcomes. We hypothesize that the modified interventions (High-Magnitude CM and Shaping CM) will lead to higher rates of alcohol abstinence than the Usual CM intervention. If the condition-by-time interaction variable is significant, we will conduct planned comparisons to examine the hypothesized pattern for each outcome. Such an approach will allow us to test this set of hypotheses with specificity. We will also conduct a direct comparison of the High-Magnitude CM group and the Shaping CM group.

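### The condition-by-time gate for the Usual CM contrasts does not fit the stated primary window, and Section 4.G.2 also leaves the primary model's covariates to be chosen from trial data

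*Combined protocol and SAP*

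**What the plan says.** **Window.** Section 4.G.1 states: "We will analyze our primary and secondary outcomes longitudinally across the final 12-weeks of CM", and adds the 6-month follow-up. Sections 1, 4.B and 4.F.2 define the primary outcome the same way. Section 4.G.2 (Aims 1 and 2) instead fits the GEE over a 12-month period made up of "1 month before the baseline interview plus the 1-month induction, 4-month treatment, and 6-month follow-up periods".

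**Gate.** The same paragraph says: "If the condition-by-time interaction variable is significant, we will conduct planned comparisons to examine the hypothesized pattern for each outcome". Section 4.G.3 quotes power for planned comparisons that follow an initial omnibus test, without saying which test that is. The direct comparison of High-Magnitude with Shaping is mentioned separately and is not placed behind the gate.

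**Covariates.** Section 4.G.2 gives two rules. The first is "Variables that differ between groups at baseline and during the induction period will be used as covariates in subsequent analyses", and the screening is described as "Comparisons will use analysis of variance (ANOVA) for continuous variables and chi-square tests for categorical variables". The second adds "as will baseline measures that co-vary with the outcome measures". Neither rule has a variable list, and the only threshold in sight is the general alpha of 0.05.

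**Randomization.** Section 4.D.3 states: "We will stratify across the following variables: 1) study site, 2) gender, and 3) baseline EtG level > 1,000 ng/mL". No analysis section commits these factors to the model; sex appears only as a moderator. Under Section 4.D.2, participants must "attain an average EtG score of > 499 ng/mL" over induction to be randomized.

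**The concern.** The gate decides whether the hypothesised contrasts of the two modified arms with Usual CM are tested. What a condition-by-time test detects depends on which periods count as outcome time. If the pre-treatment months are included, a treatment effect appears as an interaction. If they are excluded, only a *change* in the effect does. Aim 1 hopes for higher abstinence in treatment and in follow-up, so a steady benefit is a natural form of success. That is the pattern the gate misses in the stated primary window.

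The two descriptions also give induction EtG three roles: eligibility filter (4.D.2), candidate covariate (4.G.2) and outcome time (the 12-month GEE). The 12-month window includes weeks 5-8 as well, when the Shaping arm works under a different reinforcement criterion (4.E.6).

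The covariate rules are a smaller matter. Between randomized arms, observed differences are chance. Factors balanced by stratification are the least likely to be picked by the first rule. The second rule cannot be applied until outcome data exist. The primary model, and with a logit link the quantity it estimates, is therefore not known in advance. The rules also differ in scope: the first names baseline and induction, the second only baseline, so it is unclear whether induction EtG may enter through the second.

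**Working it through.** **1. The plan's own figures.** Attrition reproduces: 180 / (1 - 0.25) = 240. The 83% power for an 8-point difference in the planned comparisons (4.G.3) cannot be reproduced, because neither base rate nor within-person correlation is given. One bound needs neither: P(gate opens and contrast is significant) ≤ P(gate opens). If the omnibus test is condition-by-time in the primary window, 83% cannot hold for a steady effect. If it is a condition test, this bound is no obstacle.

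**2. Gate in the primary window.** From the documents: 240 randomized (80 per arm if equal), 12 weeks x 3 = 36 treatment samples and 3 follow-up samples (4.F.2), alpha 0.05. Assumed: 32% negative samples in Usual CM, 46% in both modified arms, person-level SD 2.2 on the logit scale, no missing data.
- Log odds ratio in treatment: ln(0.46/0.54) - ln(0.32/0.68) = -0.16 + 0.75 = 0.59.
- At follow-up, if the effect is steady: 0.59. Interaction: 0.59 - 0.59 = 0, so the gate opens at about alpha.
- Simulated: 4.7% to 5.8%. A second model (beta-binomial, 20% versus 32%, correlation 0.3 to 0.6, linear time, 60 or 80 per arm) gives 5% to 6%. The zero interaction does not depend on the assumed rates.
- If the effect halves at follow-up, the gate opens 48% to 50% of the time. If it vanishes, 97%.

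**3. Gate over 12 months.** Table 4 schedules no EtG before week 0, so the EtG periods are induction (12 samples), weeks 5-8 (12), weeks 9-20 (36) and follow-up (3). Further assumption: 8% negative in induction; periods are categorical.
- Benefit present from week 5 in both modified arms: about 53%.
- Shaping benefit starting only at week 9: near 100%.
- Time coding matters too. In the second model, with induction added to the primary window, linear time gives 35% to 48% and a pre/post contrast 49% to 84%.

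**4. A condition test instead.** A two-degree-of-freedom condition test averaged per sample over weeks 9-20 plus follow-up, with a fixed covariate set and the inputs of step 2, opens 84.1% to 88.8% of the time for a steady effect and 78.5% to 82.4% if the effect vanishes at follow-up. Per-sample averaging gives follow-up 3/39 = 7.7% of the weight.

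**5. Covariates.** Assumed: 24 candidates; induction EtG explains 5%, 10% or 16% of person-level variance among those randomized; the second rule is applied at 0.05. The documents do not give this strength: Section 2.B.7 compares means below 500 with means above 499 ng/mL, and only the latter group is randomized.
- The first rule picked a stratification factor in 0 of 28,000 simulated trials, yet flagged at least one variable in 62% to 64%. As a check, 20 independent tests give 1 - 0.95^20 = 64%.
- Pairwise power, steady effect: fixed set (strata plus log mean induction EtG) 81.6 / 82.3 / 85.4%; both rules with induction EtG eligible 80.5 / 82.1 / 84.6%; not eligible 80.0 / 80.1 / 81.5%; no adjustment 79.1 / 79.0 / 80.0%.
- Over steady, half-fading and fully fading effects, the fixed set gains 0.2 (82.3 - 82.1) to 1.1 (81.6 - 80.5) points if induction EtG is eligible. If not, it gains 1.6 (81.6 - 80.0) to 5.6 (82.5 - 76.9, half-fading) points.
- Pairwise type I error was 4.6% to 5.7% in all models. For a steady effect, the p<0.05 verdict differed between fixed set and rules in 4.7% to 6.0% of trials (7.3% to 8.8% if induction EtG is not eligible).
- The fixed-set log odds ratio exceeds the unadjusted one by 3% (0.618/0.599) to 8% (0.644/0.597), because the estimand differs.

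**The case against.** Several objections have force.

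- *The condition effect is not ignored.* Section 4.G.2 says outcomes are examined across condition, time and their interaction, and High-Magnitude versus Shaping is not gated. A reader might infer that a steady benefit could never be found. The documents do not support that: the condition effect would be reported, and over 12 months the gate can open often. What stands is that only the interaction is named as the condition for the planned comparisons.
- *The month before baseline need not be an error.* The 12-month sentence covers secondary outcomes too, and prior-30-day drinking is self-reported at entry. This is right; the difficulty is confined to EtG.
- *The covariate rules do little harm.* A reader might infer inflated type I error or bias. Mechanical use shows neither. Free choice among unadjusted, imbalance-adjusted and fully selected models would raise type I error to 0.073-0.081 in one simulation, but the plan does not describe such a choice. Reading baseline measures to include induction is at least as natural as excluding it, which puts the power cost at the low end, close to simulation error (0.35 to 0.5 point for paired gains).
- *The scenario is kinder than the plan.* It uses a 14-point effect, 240 people and no missing data; Section 4.G.3 uses 7 to 8 points and 60 per group. The 12-month gate figures and covariate gains depend on these inputs. The 5% in the primary window does not.
- *A condition gate has its own weakness* if the effect vanishes at follow-up: 78.5% to 82.4% against 97%.

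**Conclusion.** The concern holds, with its weight on the window and the gate. The sections contradict each other on the period modelled for the primary outcome, and the gate is unsuitable for the window that most of them state: a benefit constant on the log-odds scale opens it about 5% of the time. This follows from the definition of interaction. Over 12 months the answer moves between about 53% and near 100% with the onset of the Shaping effect, and also varies with time coding. Those figures rest on assumed rates, correlation and complete data. The gate simulated with induction included also rejects about 7% of the time under the null, so they are slightly flattering.

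The covariate part is secondary: a model not fixed in advance, stratification factors not committed, and a small loss of precision under assumed inputs. It should be corrected because doing so is cheap, not because it threatens validity. Overall this is a change the sponsor should make.

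**What to change.** 1. **Window.** Use weeks 9-20 plus follow-up for the primary EtG model, with induction EtG as a covariate and not an outcome time point. The 12-month description may stay for secondary self-report outcomes that have pre-baseline data.
2. **Gate.** Open the planned comparisons on a two-degree-of-freedom condition test over that window. State the weights for treatment and follow-up, report condition-by-time as secondary, and define the omnibus test in Section 4.G.3 as this same test. Items 1 and 2 must change together: aligning the window alone would leave the 5% gate in force.
3. **Covariates.** Replace both selection rules with the stratification factors as used at randomization (saying whether baseline EtG means the week-0 value or the induction mean) plus log mean induction EtG. For Aim 2, use the stratification factors plus the outcome's own baseline value. Keep baseline comparisons descriptive. Put other covariates, including predictors of dropout, in the imputation model or in named sensitivity analyses.

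The cost is analysis-plan wording; all variables are already collected. The downside is about four degrees of freedom per model, some overlap between the EtG stratum and induction EtG, and lower sensitivity than condition-by-time if the effect disappears at follow-up.

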**2.B.6 CM Is Effective.** As described in the Appendix, CM participants were **3.1 times** (95% CI=2.2-4.5) more likely than controls to submit **alcohol-negative samples** during treatment. The duration of alcohol abstinence (defined as the number of consecutive alcohol-negative EtG samples) **was twice as long in the CM group as in controls** (CM M=8.6, SD=12.6, controls M=4.1, SD=1.2, p<0.05). The mean EtG level (409 ng/mL, SE=40 ng/mL) in CM participants was lower than in controls (735 ng/mL, SE=41 ng/mL, p< 0.05). CM participants reported fewer days of alcohol use in treatment (M=3.7, SE=1.6) and follow-up (M=3.3, SE=1.4), compared to controls (treatment M=12.0, SE=1.5, p<0.05, follow-up M=10.7, SE=1.4, p<0.05). Those in CM were less likely to than controls to report heavy drinking in treatment (OR=3.5, 95% CI=2.3-5.2) and follow-up (OR=4.9, 95% CI=1.8-13.5). CM participants were more likely than controls to submit stimulant-negative urine samples during treatment (OR=3.2, 95% CI=2.0-5.1) and follow-up (OR=4.6, 95% CI=1.2-17.1), and smoking-negative carbon monoxide breath samples during treatment (OR=5.4, 95% CI=1.9-15.0).

**2.B.7 Heavy Drinkers do Not Respond to Usual CM.** The efficacy of CM was associated with average EtG levels during a 4-week induction (i.e., pre-randomization) period. CM participants with mean pre-randomization EtG < 500 ng/mL (light drinking) attained continuous abstinence that was **2.3 times longer** than those with mean EtG > 499 ng/mL (recent heavy drinking; p=0.03; see Table 1). This equals 2 weeks of additional abstinence. Light drinkers also attained a duration of continuous drug abstinence that was 5 times longer (M=10.7, SD=9.5) than heavy drinkers (M=1.9, SD=3.0). Finally, CM participants with pre-treatment EtG > 499 ng/mL had levels of abstinence similar to controls, indicating that they did not respond to CM.

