Executive functioning: NIH Toolbox/MCQ (cognitive tests/self-report)	✓			
Alcohol incentive salience (self-report/cognitive tests)	✓			
Adverse Events				
Alcohol withdrawal: SHOT (interviewer rating)	✓	3x / Wk	3x / Wk	Every visit
Participant safety (self-report/observation)	✓	3x / Wk	3x / Wk	Every visit

**4.F.2 Measures Overview.** Baseline data will include assessment of eligibility criteria and measures for Aims 1-4. Our primary outcome (Aim 1) is biochemically confirmed alcohol abstinence, measured 3 times per week during the final 12 weeks of the treatment period (weeks 9-20) and 3 times total during the 6-month follow-up period. Aim 2 outcomes will be collected in a similar fashion. Cost data will be collected for 12 months before and after randomization. Aim 3 outcomes consist primarily of self-reported use of non-study

healthcare resources, QALYs, days of alcohol abstinence, and heavy drinking days averted. We will collect data on each ANA domain to test for predictors of alcohol abstinence during CM interventions.

**4.F.3 Eligibility Criteria.** Age and frequency of recent drinking will be assessed by phone screening. The Structured Clinical Interview for DSM-5 (SCID-5) interview, clinical trials version, will be administered to assess diagnostic inclusion (SMI, AUDs) and exclusion criteria. Competency to provide informed consent will be assessed as described in Section 4.C.2.

**4.F.4 Primary Outcome.** Our primary outcome will be alcohol abstinence during the last 3 months of treatment and the 6-month follow-up period. At each study visit, urine samples will be collected and analyzed onsite for EtG by using the [commercially available Diagnostic Reagents Incorporated EtG immunoassay on an Indiko Bench Top Analyzer (ThermoFischer Scientific, Freemont, CA).] We will use the assay to create a binary indicator of alcohol use defined by EtG < 100 ng/mL. That threshold was used in our first funding period and in our ongoing CM trials. While it is not associated with false positives due to non-beverage alcohol exposure, we will ask participants to abstain from using all alcohol-containing products, like hand sanitizer.

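### The derived count of abstinence periods is tested for superiority but has no consistent direction, so sustained abstinence can score below intermittent drinking

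*Combined protocol and SAP*

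**What the plan says.** Section 4.G.2 (Aims 1 and 2) starts from a result per sample, "binary outcome: EtG < 100 ng/mL or EtG > 100 ng/mL", and names five measures as examples of what will be derived from it. The third is "3) total number of periods of alcohol abstinence". The longest spell of abstinence, the time to first abstinence and the time to relapse are listed separately. All five are to be examined by condition, time and their interaction "to determine whether one condition is superior to the others in promoting discontinuation of alcohol use". The stated hypothesis is that the two modified conditions "will lead to higher rates of alcohol abstinence than the Usual CM intervention". Section 4.G.1 adds: "Our alpha threshold for statistical significance will be 0.05".

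Section 4.G.2 gives no definition of a period, no minimum length, no direction of benefit and no rule for a missed sample in this count. The nearest definition is in section 2.B.6, where duration of abstinence in the earlier trial is "defined as the number of consecutive alcohol-negative EtG samples". Section 4.F.2 sets three samples a week in weeks 9-20, and then "3 times total during the 6-month follow-up period".

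**The concern.** A measure used to decide superiority must have a better end. A count of separate abstinent runs has none. It is low for someone who never stops drinking and also low for someone who stops and never resumes. It is highest for someone who stops and restarts repeatedly, because each relapse followed by a negative sample opens a new run.

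The trial hopes that modified CM will turn interrupted abstinence into lasting abstinence. That change merges several runs into one and lowers the count. Read as a superiority measure, the result could then point towards Usual CM although the modified condition had done better.

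**Working it through.** **No stated figure to reproduce.** The documents give no expected value, power or sample size for this count. The sampling grid can be checked: 16 treatment weeks with 3 samples a week and draws rising from 3 to 18 give 3 × 168 = 504, and from 14 to 29 give 3 × 344 = 1,032. Both match Table 3.

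**Inputs.**
- Samples in weeks 9-20: 3 × 12 = 36 (section 4.F.2).
- A period is a run of consecutive negative samples (borrowed from section 2.B.6; an assumption for this outcome).
- Share of negative samples p and lag-1 correlation r: not given, so varied below.

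**Fixed cases, 36 samples.** Never negative: 0. Always negative: 1. Strict alternation: 36 / 2 = 18. Adding the three follow-up samples (39) raises that ceiling to 20.

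**Expected count.** A new run starts when the first sample is negative (probability p) or when a positive is followed by a negative. The latter has probability (1 − p) × p(1 − r) at each of the 35 transitions. So

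E = p + 35p(1 − p)(1 − r).

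| p | r = 0.4 | r = 0.6 | r = 0.8 |
|---|---|---|---|
| 0.2 | | 0.2 + 2.24 = 2.44 | |
| 0.5 | 0.5 + 5.25 = 5.75 | 0.5 + 3.50 = 4.00 | 0.5 + 1.75 = 2.25 |
| 0.8 | 0.8 + 3.36 = 4.16 | 0.8 + 2.24 = 3.04 | 0.8 + 1.12 = 1.92 |
| 0.9 | | 0.9 + 1.26 = 2.16 | |
| 1.0 | 1.00 | 1.00 | 1.00 |

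Setting the derivative to zero puts the peak at p = 0.5 + 1/[70(1 − r)]. That is 0.51 for r = 0, 0.54 for r = 0.6 and 0.64 for r = 0.9. At r = 0.6, moving from 50% to 80% negative lowers the count from 4.00 to 3.04, a fall of 24%.

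**Mixed arms (assumed, r = 0.6).** The arm average need not exceed 50%.
- Arm A: 40% never negative, 60% intermittent at p = 0.5. Abstinence 0.6 × 0.5 = 30%; mean count 0.6 × 4.0 = 2.4.
- Arm B: as A, but one third of the intermittent drinkers become fully abstinent. Abstinence 0.4 × 0.5 + 0.2 = 40%; mean count 0.4 × 4.0 + 0.2 × 1 = 1.8.

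Arm B has more abstinence and the lower count.

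**Minimum run length.** If a period needs at least m negatives, the ceiling is the whole part of 37/(m + 1): 12, 9, 5 and 2 for m = 2, 3, 6 and 12. Full abstinence still scores 1, so the reversal remains.

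**Simulated test.** 60 per arm, two-sided t-test at 0.05 (the plan does not state sidedness), r = 0.5, beta-distributed participant rates with concentration 2, 1,500 replicates.

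| Negative share, worse vs better arm | Favours better arm | Favours worse arm |
|---|---|---|
| 0.20 vs 0.32 | 56% | 0% |
| 0.50 vs 0.62 | 1% | 3% |
| 0.60 vs 0.72 | 0.1% | 18% |
| 0.70 vs 0.85 | 0% | 73% |

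The last figure ranges from 45% to 91% for concentrations 1 to 4.

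**The case against.** The strongest reply is that this sample will sit where the count behaves. Randomized participants must have mean induction EtG above 499 ng/mL. In the earlier trial such participants under CM averaged a longest run of only 4.6 negatives (Table 1), and section 2.B.7 describes them as not responding. Below about 50% negative samples the count rises with abstinence when participants are alike, and the simulation at 0.20 vs 0.32 shows no reversals. Differences of the size the plan is powered for also move the count little from the peak: at r = 0.6, going from 50% to 58% changes it from 4.00 to 3.99. This stands as a limit on how often reversal would occur. It does not give the measure a direction: at 50% it is nearly blind to improvement, and mixed arms can reverse at 30% vs 40%.

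The term is also undefined. The same paragraph speaks of heavy drinking months, so a count of abstinent weeks or months may be meant, and that would rise with abstinence. This is possible, but the text does not say it.

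A reader might infer three stronger things that the documents do not support:
- **That a score of 18 is realistic.** It is only a mathematical ceiling. Section 1 says EtG can detect drinking for up to 5 days, and samples are taken on Mondays, Wednesdays and Fridays, so strict alternation is unlikely.
- **That a missed visit splits a run and inflates the count.** No passage says so for this outcome. The reset rule in section 4.E.2 governs prize draws, and section 4.G.2 plans maximum likelihood or multiple imputation for missing data.
- **That the trial's main conclusion is at risk.** The count is one of several examples of derived measures. The other listed measures would help show that a low count reflects sustained abstinence, and none of the stated power figures or cost-effectiveness ratios uses it.

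**Conclusion.** The point holds as a minor one. If a period is a run of negative samples, the scores of 0 for never abstinent and 1 for fully abstinent are exact, and intermittent drinking scores higher, so a superiority comparison on the count has no consistent meaning. The size of any reversal depends on assumed abstinence rates, serial correlation and variation between participants. With similar participants, reversal needs abstinence above roughly one half. The documents do not predict that range, so it cannot be said that the comparison will favour the worse condition in this trial, only that it can. The primary analysis of EtG-verified abstinence by GEE is not affected.

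**What to change.** In the section 4.G.2 list, replace the item with the number of fully abstinent weeks in weeks 9-20, a week counting when all three scheduled samples have EtG < 100 ng/mL. Full abstinence scores 12 and strict alternation 0, and turning a positive sample negative can never lower the score. The same line should say how a missed sample is handled.

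Alternatively, keep the count of periods, define a period, report it descriptively as relapse cycling, and state that no superiority conclusion will be drawn from it.

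Either change costs one line of wording and needs no new data. The abstinent-week count overlaps somewhat with the other abstinence measures and gives no credit for partly abstinent weeks.
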